Hyperchloremic, non-anion gap, metabolic acidosis (ie, decreased serum bicarbonate below the normal reference range in the absence of chronic respiratory alkalosis) is associated with topiramate treatment. This metabolic acidosis is caused by renal bicarbonate loss due to the inhibitory effect of topiramate on carbonic anhydrase. Such electrolyte imbalance has been

observed with the use of topiramate in placebo-controlled clinical studies and in the post-marketing period. Generally, topiramate-induced metabolic acidosis occurs early in treatment, although cases can occur at any time during treatment. Bicarbonate decreases are usually mild to moderate (average decrease of 4 mEq/L at daily dosages of 400 mg/day in adults and at approximately 6 mg/kg/day in children); rarely, subjects can experience severe decreases, to values <10 mEq/L.³³

Some manifestations of acute or chronic metabolic acidosis may include hyperventilation, nonspecific symptoms such as fatigue and anorexia, or more severe sequelae, including cardiac arrhythmias or stupor. Chronic, untreated metabolic acidosis may increase the risk for nephrolithiasis or nephrocalcinosis, and may also result in osteopenia or osteoporosis, with an increased risk for fractures. Chronic metabolic acidosis in pediatric subjects may also reduce growth rates. A reduction in growth rate may eventually decrease the maximum height achieved. The effect of topiramate on growth and bone-related sequelae has not been systematically investigated.

Growth and Maturation

Reports have suggested that certain AEDs may adversely affect growth and maturation in some children. Body weight was evaluated among pediatric subjects 6 to 15 years of age in clinical studies with topiramate monotherapy, and in 1 of these studies (study TOPMAT-EPMN-106) body mass index (BMI) was evaluated according to Centers for Disease Control (CDC) criteria. Among pediatric subjects administered topiramate monotherapy in studies TOPMAT-EPMN-104, TOPMAT-EPMN-105, and TOPMAT-EPMN-106, mean body weight increased in the double-blind treatment phase; most subjects experienced an increase or no change in body weight. Of those with weight loss, most exhibited decreases of 1% to 9%. Adverse events of weight loss were reported in 21% of pediatric subjects but none was serious or treatment-limiting. In the open-label extension of monotherapy treatment studies TOPMAT-EPMN-104 and TOPMAT-EPMN-106, mean body weight of pediatric subjects also increased.

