1.1. Comparator Agent

Levetiracetam

Levetiracetam is indicated for use as an adjunctive therapy for POS (adults and children ≥ 1 month of age with epilepsy), PGTCs (adults and children ≥ 6 years of age with idiopathic generalized epilepsy), and myoclonic seizures (adults and children ≥ 12 years of age with juvenile myoclonic epilepsy [JME]).²⁴ The safety profile in pediatric subjects with epilepsy is summarized below.

Subjects With Partial-Onset Seizures

In pediatric subjects experiencing POS, levetiracetam is associated with somnolence, fatigue, and behavioral abnormalities.²⁴

In a double-blind, controlled study in children with epilepsy experiencing POS, 22.8% of levetiracetam-treated subjects experienced somnolence, compared with 11.3% of placebo subjects. The design of the study prevented accurately assessing dose-response effects. No subject discontinued treatment for somnolence. In about 3.0% of levetiracetam-treated subjects and in 3.1% of placebo subjects, the dosage was reduced as a result of somnolence.²⁴

Asthenia was reported in 8.9% of levetiracetam-treated subjects, compared with 3.1% of placebo subjects. No subject discontinued treatment for asthenia, but asthenia led to a dosage reduction in 3.0% of levetiracetam-treated subjects compared with 0% of placebo subjects.²⁴

A total of 37.6% of the levetiracetam-treated subjects experienced behavioral symptoms (reported as agitation, anxiety, apathy, depersonalization, depression, emotional lability, hostility, hyperkinesia, nervousness, neurosis, and personality disorder), compared with 18.6% of placebo subjects. Hostility was reported in 11.9% of levetiracetam-treated subjects, compared with 6.2% of placebo subjects. Nervousness was reported in 9.9% of levetiracetam-treated subjects, compared with 2.1% of placebo subjects. Depression was reported in 3.0% of levetiracetam-treated subjects, compared with 1.0% of placebo subjects.²⁴

A total of 3.0% of levetiracetam-treated subjects discontinued treatment due to psychotic and nonpsychotic adverse events, compared with 4.1% of placebo subjects. Overall, 10.9% of levetiracetam-treated subjects experienced behavioral symptoms associated with discontinuation or dosage reduction, compared with 6.2% of placebo subjects.²⁴

Subjects With Myoclonic Seizures

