During clinical development, the number of subjects with myoclonic seizures exposed to levetiracetam was considerably smaller than the number with partial seizures. Therefore, underreporting of certain adverse events was more likely to occur in the myoclonic seizure population. In adult and adolescent subjects experiencing myoclonic seizures, levetiracetam is associated with somnolence and behavioral abnormalities. It is expected that the events seen in POS subjects would occur in patients with JME. In a double-blind, controlled study in adults and adolescents with JME experiencing myoclonic seizures, 11.7% of levetiracetam-treated subjects experienced somnolence compared with 1.7% of placebo subjects. In 1.7% of levetiracetam-treated subjects and in 0% of placebo subjects, the dosage was reduced as a result of somnolence.

Non-psychotic behavioral disorders (reported as aggression and irritability) occurred in 5% of the levetiracetam-treated JME subjects compared with 0% of placebo subjects. Non-psychotic mood disorders (reported as depressed mood, depression, and mood swings) occurred in 6.7% of levetiracetam-treated JME subjects compared with 3.3% of placebo subjects. A total of 5.0% of levetiracetam-treated subjects had a reduction in dosage or discontinued treatment due to behavioral or psychiatric events (reported as anxiety, depressed mood, depression, irritability, and nervousness), compared with 1.7% of placebo subjects.

In a well-controlled clinical study that included both adolescent (12 to 16 years of age) and adult subjects with myoclonic seizures, the most frequently reported adverse events associated with the use of adjunctive levetiracetam, not seen at an equivalent frequency among placebo-treated subjects, were somnolence, neck pain, and pharyngitis. The different pattern of adverse events, as compared with subjects with POS, is likely due to the much smaller number of subjects in the JME study.²⁴

Subjects With Primary Generalized Tonic-Clonic Seizures

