Adverse events of clinical interest for topiramate are: effects on liver function; metabolic acidosis; effects on growth and maturation; vision abnormalities; oligohidrosis with hyperthermia and rash; hyperammonemia and encephalopathy; kidney stones; cognitive disorders; and suicidality.

Adverse events of clinical interest for levetiracetam are as listed previously, notably somnolence, asthenia, and behavior disturbances (especially hostility and nervousness).

Subjects with adverse events of special interest may be counted or listed.

Clinical Laboratory Tests

Laboratory data will be summarized by type of laboratory test. Reference ranges and markedly abnormal results (specified in the Statistical Analysis Plan) will be used in the summary of laboratory data. Descriptive statistics will be calculated for each laboratory analyte at baseline and at each scheduled time point. Changes from baseline results will be presented in pre- versus

posttreatment cross-tabulations (with classes for below, within, and above normal ranges). A listing of subjects with any laboratory results outside the reference ranges will be provided. A listing of subjects with any markedly abnormal laboratory results will also be provided.

Vital Signs

Descriptive statistics of temperature, heart rate, respiratory rate, and blood pressure (systolic and diastolic) values and changes from baseline will be summarized at each scheduled time point. The percentage of subjects with values beyond clinically important limits (using age-appropriate ranges) will be summarized.

Physical Examination/Neurologic Examination

Descriptive statistics of changes from baseline will be summarized at each scheduled time point.

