7.9. Adverse Events

Adverse events are coded to System Organ Class (SOC) and preferred terms (PT) using the Medical Dictionary for Regulatory Activities (MedDRA) coding system, version 21.1 or higher. Treatment-emergent adverse events (TEAEs) are those AEs which start or worsen after receipt of the first study drug and before the end of the REACH. REACH is defined as follows: AEs with onset date within therapeutic reach (i.e. 3 days) or SAEs/deaths with onset date within 30 days, inclusive, after end of treatment. AE's with partial onset date will be handled as follows: a missing day should be set to first of month. If month is missing the missing month should be set to January.

Summaries of TEAEs will be provided as incidence tables (number of subjects experiencing an event) by treatment group within each age group and overall (age 2-15). For each TEAE, the percentage of subjects who experience at least 1 occurrence of the given event will be summarized. Tables will be sorted by decreasing frequency in incidence (the highest to lowest incidence) first within the SOC and then the PT. Treatment-emergent serious AEs (SAEs), TEAEs leading to discontinuation, TEAEs by severity, TEAEs by relationship and TEAEs of special interest will be summarized. Adverse events of special interest for topiramate include: effects on liver function; metabolic acidosis; effects on growth and maturation; vision abnormalities; oligohidrosis, hyperthermia and secondary rash; hyperammonemia and/or encephalopathy; kidney stones; neuropsychiatric and cognitive disorders; and suicidality. Adverse events of clinical interest for levetiracetam are as listed previously, notably somnolence, asthenia, and behavior disturbances

(especially hostility and nervousness). Please see [Appendix 3](#) for the MedDRA codes for these AE of clinical interest.

A listing of AEs will also be provided.

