Appendix 3: AE of clinical interest

AETERM	AEBODSYS in MedDRA 22.0	AEDECOD (PT) In MedDRA 22.1
5' nucleotidase increased	Investigations	5' nucleotidase increased
Abulia	Psychiatric disorders	Abulia
Accommodation disorder	Eye disorders	Accommodation disorder
Acidosis	Metabolism and nutrition disorders	Acidosis
Acidosis hyperchloraemic	Metabolism and nutrition disorders	Acidosis hyperchloraemic
Acquired epidermolysis bullosa	Skin and subcutaneous tissue disorders	Acquired epidermolysis bullosa
Acquired pigmented retinopathy	Injury, poisoning and procedural complications	Acquired pigmented retinopathy
Activation syndrome	Psychiatric disorders	Activation syndrome
Acute generalised exanthematous pustulosis	Skin and subcutaneous tissue disorders	Acute generalised exanthematous pustulosis
Acute hepatic failure	Hepatobiliary disorders	Acute hepatic failure
Renal failure acute	Renal and urinary disorders	Acute kidney injury
Adjustment disorder with anxiety	Psychiatric disorders	Adjustment disorder with anxiety
Adjustment disorder with depressed mood	Psychiatric disorders	Adjustment disorder with depressed mood
Adjustment disorder with mixed anxiety and depressed mood	Psychiatric disorders	Adjustment disorder with mixed anxiety and depressed mood
Adjustment disorder with mixed anxiety and depressed mood	Psychiatric disorders	Adjustment disorder with mixed anxiety and depressed mood
Affect lability	Psychiatric disorders	Affect lability
Agitated depression	Psychiatric disorders	Agitated depression
Agitation	Psychiatric disorders	Agitation
Alanine aminotransferase abnormal	Investigations	Alanine aminotransferase abnormal
Alanine aminotransferase increased	Investigations	Alanine aminotransferase increased
Albumin urine present	Investigations	Albumin urine present
Alpha 1 foetoprotein abnormal	Investigations	Alpha 1 foetoprotein abnormal
Alpha 1 foetoprotein increased	Investigations	Alpha 1 foetoprotein increased

Alpha 1 globulin increased	Investigations	Alpha 1 globulin increased
Alpha 2 globulin increased	Investigations	Alpha 2 globulin increased
Alpha globulin increased	Investigations	Alpha globulin increased
Alpha-2 macroglobulin increased	Investigations	Alpha-2 macroglobulin increased
Altered state of consciousness	Nervous system disorders	Altered state of consciousness
Altered visual depth perception	Eye disorders	Altered visual depth perception
Amaurosis	Eye disorders	Amaurosis
Amaurosis fugax	Eye disorders	Amaurosis fugax

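### The SAP names hostility as a levetiracetam event of interest, but Appendix 3, which is meant to hold the terms, omits Hostility, Aggression and Irritability

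*SAP*

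**What the plan says.** SAP 7.9 plans several adverse event summaries, among them that "TEAEs by relationship and TEAEs of special interest will be summarized". It then gives one set of categories for topiramate and another for levetiracetam. The levetiracetam set is somnolence, asthenia and behavior disturbances, "especially hostility and nervousness". Protocol 11.4 has the same wording: "notably somnolence, asthenia, and behavior disturbances (especially hostility and nervousness". SAP 7.9 next sends the reader to Appendix 3 "for the MedDRA codes for these AE of clinical interest". That appendix, headed "Appendix 3: AE of clinical interest", is a single table of reported terms, system organ classes and preferred terms. Its rows carry no label for drug or event category.

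Protocol 1.1 gives the background for levetiracetam. In the pediatric partial-onset study, "Hostility was reported in 11.9% of levetiracetam-treated subjects, compared with 6.2% of placebo subjects". In the juvenile myoclonic epilepsy study, "Non-psychotic behavioral disorders (reported as aggression and irritability") occurred in 5% on levetiracetam and 0% on placebo.

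**The concern.** A summary of events of interest is normally programmed from a term list, and an event coded to a term that is not on the list does not enter the summary. Here the text names hostility first among the behavior disturbances to be watched on levetiracetam, and the list built to capture those events does not contain it. Aggression and irritability belong to the same named category, and the protocol reports them on this drug. A reader who turns to the special-interest table for levetiracetam's behavioral harms would see nervousness but not hostility, aggression or irritability under their own terms, and nothing in the table would show that they had been left out.

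**Working it through.** The check is mainly a reading of Appendix 3 against SAP 7.9; the arithmetic only gives scale.

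**Step 1. Terms named or covered by SAP 7.9, against the list.** Appendix 3 is close to alphabetical by preferred term. Each gap below has its neighbours on both sides.

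| Term | Basis | In Appendix 3? | Neighbouring rows |
|---|---|---|---|
| Somnolence | named in SAP 7.9 | yes | |
| Asthenia | named in SAP 7.9 | yes | |
| Nervousness | named in SAP 7.9 | yes | |
| Hostility | named in SAP 7.9 | no | Homocysteine urine present, Hot flush |
| Aggression | behavior disturbance; Protocol 1.1 | no | Affect lability, Agitated depression |
| Irritability | behavior disturbance; Protocol 1.1 | no | Iritis, Ischaemic hepatitis |

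The three absent terms appear in neither the reported-term column nor the preferred-term column. Because the neighbours are present, a lost page does not explain the gaps. Of the four events that SAP 7.9 names for levetiracetam, three are listed and one is not.

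**Step 2. Scale, by assumption.** Inputs:
- hostility rate p = 0.119 on levetiracetam (Protocol 1.1, a different study);
- aggression or irritability p = 0.05 (Protocol 1.1, juvenile myoclonic epilepsy study);
- planned 141 randomized and 100 completed per arm (SAP 2.4).

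SAP section 1 says enrollment was stopped early, and the documents do not give the final arm sizes. I therefore assume n from 30 to 141. Expected subjects = n × p, and the chance of at least one = 1 − (1 − p)^n.

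| n per arm | Hostility, n × 0.119 | Chance of at least one | Aggression or irritability, n × 0.05 |
|---|---|---|---|
| 30 | 3.6 | 1 − 0.881^30 = 0.978 | 1.5 |
| 50 | 5.95 | 0.998 | 2.5 |
| 100 | 11.9 | >0.999 | 5.0 |
| 141 | 16.8 | >0.999 | 7.05 |

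These are expected reports that the list would not pick up under those terms. The plan states no figure of its own to reproduce.

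**The case against.** The strongest reply is that little is lost. SAP 7.9 tabulates every treatment-emergent event by system organ class and preferred term, by treatment within age group and overall, and lists all adverse events. SAP section 7 plans no formal testing. Protocol 11.4 says only that subjects with events of special interest may be counted or listed. Aggressive behavior is also measured directly, through the CBCL Aggressive Behavior and Externalizing domains (SAP 7.8). All of this stands, and it confines the defect to one summary.

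It follows that a reader might infer a biased safety comparison between the drugs, and the documents do not support that. The same untagged list applies to both arms, and the full event tables allow the comparison to be made.

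A reader might also infer that about 12 children would go missing. That takes 100 planned completers per arm in a trial whose enrollment was stopped, and borrows a rate from another study in which placebo subjects had 6.2%. The 5% for aggression and irritability is weaker still, since it comes from adults and adolescents with myoclonic seizures, which Protocol 4.2 excludes. A child with hostility who also had agitation, anxiety or nervousness would still enter a subject-level count through those listed terms.

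Third, a reader might call the absence of Osteopenia the same error. Protocol section 1 says that chronic acidosis "may also result in osteopenia or osteoporosis, with an increased risk for fractures", and Appendix 3 has Osteoporosis and Osteomalacia without it. But neither SAP 7.9 nor Protocol 11.4 names a bone category among the events of interest, and bone loss is assessed by DEXA (SAP 7.4). The gap is untidy, not a contradiction.

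Finally, SAP 7.9 uses special interest for topiramate and clinical interest for levetiracetam, so one could argue that the special-interest table was never meant to hold levetiracetam events. The reference to Appendix 3 follows directly on the levetiracetam sentence, and Nervousness, Somnolence and Asthenia are in the list, so the text does not bear that reading out. The loose wording is itself a reason to tag the terms.

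**Conclusion.** The point holds in a limited form. For Hostility the SAP contradicts itself: the text names the event and the list meant to capture it leaves it out. For Aggression and Irritability the list is incomplete against a category that the text names, which is a weaker finding because neither is named there individually. The effect is an incomplete special-interest summary for levetiracetam behavioral events, with the full event tables and the listing unaffected.

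The size cannot be fixed from the documents. The range of roughly 4 to 17 subjects with hostility rests on two assumptions: that 11.9% carries over to this trial, and that each arm has 30 to 141 subjects. The defect itself does not depend on that range.

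**What to change.** Add Hostility, Aggression and Irritability to Appendix 3 before the special-interest table is run, after confirming each as a preferred term in the MedDRA version used for coding. Tag every row with its drug and its event category as named in SAP 7.9, and state in 7.9 which tags feed which table, using one expression for events of interest throughout. Osteopenia may be added beside Osteoporosis and Osteomalacia for consistency.

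The cost is an edit to a lookup list and a new column in it. No data collection or model changes. The documents do not say whether the table has already been produced; if it has, the cost also includes one rerun.

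If the list is left as it is, the report should say under the table that hostility, aggression and irritability are not included in it and point to the overall event table.

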7.10. Clinical Laboratory Tests

Figures of the mean change from screening (+/- Standard Error) values in continuous hematology, urinalysis and serum chemistry laboratory parameters will be presented by visit. The observed and change from baseline values of lab parameters will also be summarized by visit. For calculation, the signs “<” or “>” will be removed and resulting numerical value will be used. The reference ranges for labs from the SAP will be used, not the reference ranges provided from the Covance.

The shift table of pre- vs. post-treatment with classes for below, within, and above normal ranges will be presented.

The number and percentage of subjects with markedly abnormal (low, high) laboratory hematology, urinalysis/24-hour urine and serum chemistry parameters during the study (from treatment start to 30 days after last dose or the end of treatment visit date, whichever is later) that were not present at baseline will be provided. [Appendix 2](#) presents the markedly abnormal criteria. The conversion factors for 25 Vitamin D, 1, 25 Vitamin D and PTH are also listed.

The laboratory data will be listed. The subjects with any laboratory results outside the reference ranges and the subjects with any markedly abnormal laboratory results will be listed.

